## 6.2. Measures to Minimize Bias: Randomization and Blinding

**Sequence:** A randomization sequence will be generated in a computer program and associated with predefined rows of unique patient identification numbers and inserted into the electronic data capture system (EDCS). After the participant has consented the ambulatory team will be informed and will randomize the participant using the EDCS.

Implementation; The randomization list will be produced by the CTU at OUH.

**Blinding:** This is an open-label, randomized controlled trial with a plasma arm administered as a transfusion, and all participants and staff will thus know the intervention to which the patient is allocated.

## 6.3. Study Intervention Compliance

When participants are dosed at the nursing homes, they will receive study intervention directly from the ambulatory team. The date and time of each dose administered in the nursing home will be recorded in the source documents and recorded. The dose of study intervention and study participant identification will be confirmed at the time of dosing by a member of the study site staff other than the person administering the study intervention.

# 6.4. Dose Modification

All participants will be evaluated before inclusion and should be eligible for receiving the maximum volume of 300ml plasma. In case of adverse events, transfusion will be terminated, possibly resulting in a dose reduction. The actual dose of the study intervention will then be recorded and these participants will be excluded from the PPS.

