	
 
Exclusion criteria
 
1. Included in any other interventional study for the treatment of COVID-19
 
2. Allergic reactions to plasma products
 
3. Acute severe co-morbidity
 

	
 
4. Estimated life-expectancy <90 days prior to symptomatic COVID-19 as assessed by attending clinician.
 
5. Other reasons where the attending clinician deems trial participation to be against the best interest of the patient
 
	
Intervention	SARS-CoV-2 convalescent plasma (1 unit; ~200-300 mL) from blood donors who were diagnosed and have recovered from COVID-19 infection, tested and released according to criteria from the Norwegian Health Directorate.	
Description of groups	Group 1: Standard of care + convalescent plasma given according to criteria	
Criteria for interruption	Group 2: Standard of care There will be one interim analysis for efficacy after half of the patients (n=253) have completed the first 28 days of follow-up. The study will be stopped if the interim analysis demonstrates superiority of the intervention.	
	The steering committee can decide to interrupt the study early if the data monitoring committee recommends discontinuation for safety reasons	
Study duration	1. July 2020 – 30. June 2021	
Recruitment	To support the recruitment for the study, all COVID-19 RT-PCR confirmed patients who are or will be admitted to nursing homes are reported to the principal investigator. This will initiate the process to engage with the patient and / or relatives to offer participation.	
Supportive treatment allowed	Guidelines for the treatment of COVID-19 in nursing homes for this patient group are described by the Norwegian Institute of Public Health and local health authorities. The medical professionals responsible at the nursing home are responsible for providing the health care considered to be professionally required regardless of the purpose of the study.	
Participants' timeframe	The events in which study participants are planned to be engaged are described in section "Schedule of activities". Briefly, consent and enrolment will take place within 2 days of notification of the study team for patients fulfilling the case definition for a confirmed COVID-19 patient.	

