## 4.3 Justification for dose

The suggested dosing of SARS-CoV-2 convalescent plasma for transfusion is 1 unit; ~200-350 mL. This is based on the volume of available plasma drawn from donors in one unit, and from a prior study of SARS-CoV-1 patients in 2005 showing clinical benefit at median 291 mL plasma administered per patient.

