## 5.3. Study Intervention and Concomitant Therapy

Convalescent plasma will be collected from volunteer non-paid donors who recovered from a CoV-2 infection. Collection volume will be split to therapeutic units of 200-300 ml. Previous medical therapy will be continued with no interruption.

	Т		
ARM Name	COVID-19 convalescent plasma		
Intervention	ISBT E9735 CONVALESCENT PLASMA CPD/XX/<=-18C COVID-19		
Name	ISBT E9736 Apheresis CONVALESCENT PLASMA CPD/XX/<=-18C COVID-19		
	ISBT E9754 Apheresis CONVALESCENT PLASMA ACD-A/XX/<=-18C 1st container COVID-19		
	ISBT E9755 Apheresis CONVALESCENT PLASMA ACD-A/XX/<=-18C 2nd container COVID-19		
	ISBT E9756 Apheresis CONVALESCENT PLASMA ACD-A/XX/<=-18C 3rd container COVID-19		
	ISBT E9757 Apheresis CONVALESCENT PLASMA ACD-A/XX/<=-18C 4th container COVID-19		
Туре	Biologic		
Dose Formulation	200-300 ml		
Unit Dose Strength(s)	High titer, defined as virus neutralization assay titer >1:160 or equivalent in accordance with EBA (to be confirmed)		
Dosage Level(s)	1 dose at inclusion		
Route of Administration	I.V. transfusion		
Use	Clinical indication		
IMP and NIMP	Investigational Medicinal product (IMP)		
Sourcing	COVID-19 convalescent plasma from voluntary non-paid donors at the following Norwegian blood banks: Oslo University Hospital, Haukeland University Hospital, St. Olav's Hospital		
Packaging and Labeling	Following local SOP for plasma-labeling, using the correct ISBT code		

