# 6. Study Intervention Administered

# 6.1. Preparation/Handling/Storage/Accountability

The study intervention will be manufactured at collaborative blood bank units according to specified procedures. Briefly, potential donors of convalescent plasma will be evaluated at the blood-bank according to local SOP for plasma donors, regulated by "Blodforskriften". Male donors with previous transfusion history and all female donors will be screened for HLA I and HLA II antibodies. As a rule, plasma will be collected by apheresis in volumes of 600-850ml

dependent on body weight, and later split into therapeutic units of 200-350 ml before freezing according to local SOP. Plasma derived from a full-blood donation may also be used.

At the coordinating institution

- 1. The investigator or designee must confirm that appropriate temperature conditions have been maintained during transit for all study intervention received and any discrepancies are reported and resolved before use of the study intervention.
- 2. All study intervention must be stored in a secure, environmentally controlled, and monitored (manual or automated) area in accordance with the labeled storage conditions with access limited to the ambulatory team.
- 3. Only participants enrolled in the study may receive study intervention and only authorized site staff may supply or administer study intervention. Administration will follow SOP for transfusion. Blood pressure, pulse, respiratory frequency and temperature will be taken at pre-specified time-points (before transfusion, at the end of transfusion, 15 minutes after transfusion and 1 hour after transfusion.
- 4. Authorized site staff must monitor participants closely for 1 hour after study intervention for signs of adverse events. SAEs (Section 8.3) and other serious events (Section 8.3.5) will be reported immediately to the Medical Monitor, and an adverse events form will be recorded at the end of the study participation.
- 5. The coordinating investigator is responsible for study intervention accountability, reconciliation, and record maintenance (i.e., receipt, reconciliation, and final disposition records).

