## 9.3.2. Analyses Sets

The statistical analyses will be performed on the Full Analysis Set (FAS), which will contain all patients with sufficient data to allow inclusion in the analyses, as randomized. The FAS analyses thereby comply with the intention to treat principle.

A secondary analysis of the primary outcome will be performed on a Per Protocol Set (PPS), where patients who did not receive the entire plasma treatment are excluded.

The FAS and the PPS will be described in detail in the SAP.

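### Sections 4.3 and 6.1 allow plasma units of up to 350 mL, while the synopsis, Section 5.3 and the pre-inclusion evaluation in Section 6.4 stop at 300 mL

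*Protocol*

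**What the plan says.** The treatment is one unit of convalescent plasma, given once. Five places in the protocol give its volume, and they fall into two groups.

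*Up to 300 mL*
- Synopsis (Section 1.1), intervention row: "SARS-CoV-2 convalescent plasma (1 unit; ~200-300 mL) from blood donors".
- Section 5.3: "Collection volume will be split to therapeutic units of 200-300 ml". The dose row of the table in that section repeats this range.
- Section 6.4, on the assessment made ahead of inclusion: participants "should be eligible for receiving the maximum volume of 300ml plasma".

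*Up to 350 mL*
- Section 4.3: "The suggested dosing of SARS-CoV-2 convalescent plasma for transfusion is 1 unit; ~200-350 mL".
- Section 6.1, on what the blood banks produce: apheresis plasma, collected in volumes of 600-850 mL, is "later split into therapeutic units of 200-350 ml before freezing".

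The per-protocol set is described without a volume. Section 6.4 removes participants whose transfusion was ended because of an adverse event. Section 9.3.2 states that "patients who did not receive the entire plasma treatment are excluded" and leaves the detailed definition to the SAP.

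**The concern.** Different people act on the two groups of passages. Blood banks prepare units under Section 6.1. The study team assesses patients under Section 6.4, the only place where the protocol ties a patient's suitability to a volume. If the top of the preparation range is above the volume named in that assessment, a patient can be assessed for one volume and supplied with a larger one, with every step in line with some part of the protocol.

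The protocol itself makes volume relevant. Its risk table (Section 2.3) notes a raised risk of transfusion complications in the elderly, and Sections 6.5 and 10.4 treat circulatory overload as an adverse event and a reaction of special interest. At stake is a clear specification of the study product and an evaluation that matches it. The main statistical inference is not at stake.

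**Working it through.** No sample size, power or alpha figure depends on the volume, so the check is a comparison of the stated volumes and some arithmetic on the collection figures.

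**Inputs**

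| Source (Protocol) | Stated volume |
|---|---|
| 1.1 Synopsis | about 200-300 mL, one unit |
| 4.3 Justification for dose | about 200-350 mL, one unit |
| 5.3 text and table | 200-300 mL |
| 6.1 collection by apheresis | 600-850 mL |
| 6.1 unit after splitting | 200-350 mL |
| 6.4 evaluation | maximum 300 mL |

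**Step 1: how many specifications are there?** A range of 200-300 mL and a maximum of 300 mL agree, so Sections 1.1, 5.3 and 6.4 form one specification. Sections 4.3 and 6.1 form the other. There are two, and they differ only at the upper end.

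**Step 2: size of the gap.** Largest permitted unit minus stated maximum: 350 - 300 = 50 mL. Relative to the maximum: 50 / 300 = 16.7%.

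**Step 3: can units above 300 mL arise from the stated collection volumes?** Take a collection of V mL split into k equal units of V / k.
- k = 2: a unit exceeds 300 mL but stays within 350 mL when 300 < V / 2 ≤ 350, that is 600 < V ≤ 700. For example, 650 / 2 = 325 mL and 700 / 2 = 350 mL. Above 700 mL a two-way split falls outside both ranges (750 / 2 = 375 mL).
- k = 3: 600 / 3 = 200 mL and 850 / 3 = 283 mL. Every unit lies inside both ranges.
- k = 4: 800 / 4 = 200 mL and 850 / 4 = 212.5 mL lie inside both ranges. Smaller collections fall below both (700 / 4 = 175 mL).

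Units above 300 mL are therefore possible under Section 6.1, but the collection volumes do not force them. Equal splitting is my assumption; Section 6.1 refers to local procedure. Unequal splits can also produce them: 850 = 350 + 250 + 250.

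**Step 4: does another passage settle it?**
- Section 6.3 has a second staff member confirm the dose at the time of dosing, but the protocol gives two ranges to confirm it against.
- Section 6.5 treats overdose as not applicable, so it gives no rule for a unit above the Section 6.4 maximum.
- The earlier study cited in Section 4.3 had a median of 291 mL, which lies inside both ranges.
- The synopsis and Section 4.3 mark their ranges as approximate, but Sections 5.3 and 6.1 give the two different ranges without that mark, and Section 6.4 speaks of a maximum.

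None of these resolves the conflict.

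**The case against.** The strongest case on the other side is that this is a small wording mismatch with little practical effect.

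- *Few units may be affected.* An equal three-way split keeps every unit within 300 mL, and the product codes in Section 5.3 run to a third and fourth container, so splits beyond two are foreseen. This stands. The share of units above 300 mL is not given and could be zero. A reader might infer that the whole plasma arm (about 253 patients, half of 506) is exposed, but the protocol does not support that; only recipients of units above 300 mL are concerned.
- *Section 6.4 is not a formal tolerance test.* The numbered criteria in Sections 5.1 and 5.2 contain no volume criterion, and overload is covered by vital signs around the transfusion, an hour of close monitoring, termination on adverse events and the reaction definitions in Section 10.4. This also stands, and nothing in the protocol quantifies the added risk from 50 mL. It does not remove the fact that the one volume named in the evaluation is below the top of the preparation range.
- *The per-protocol set is not undermined.* A reader might infer that a patient given 300 mL of a 350 mL unit is per-protocol under one passage and excluded under another. The text does not support this. Neither Section 6.4 nor Section 9.3.2 sets a threshold in mL, the treatment is one unit, and a completed unit of any size can be read as complete. Doubt would arise only if a unit above 300 mL were deliberately stopped at 300 mL without an adverse event. No passage describes that practice, and Section 9.3.2 leaves the detail to the SAP, which is not at hand.

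**Conclusion.** The contradiction holds and nothing else in the protocol resolves it. Sections 4.3 and 6.1 permit units that Sections 1.1, 5.3 and 6.4 do not, by up to 50 mL (16.7% of the stated maximum). That figure is the worst case for a single unit, not an expected excess, and the number of patients concerned cannot be derived from the protocol.

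The primary analysis on the full analysis set, the 121 required deaths and the total of 506 patients do not depend on the volume. No defect in the per-protocol definition is claimed. The point is still more than clerical, because the figure is the dose of the study product, blood banks and the ambulatory team act on it, and the protocol itself describes the population as at higher risk of transfusion complications. The conclusion rests only on the stated volumes; the equal-split assumption serves to show that units above 300 mL are feasible.

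**What to change.** The sponsor should reconcile Sections 1.1, 4.3, 5.3, 6.1 and 6.4 to one volume range, used in the same terms throughout. The evaluation in Section 6.4 and the preparation text in Section 6.1 should then refer to that same range, so that every unit that can be supplied is covered by the evaluation. The dose check at administration in Section 6.3 would then have a single reference. Which figure applies is for the sponsor to decide; this review does not propose one.

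The cost is a wording amendment to the protocol, with ethics committee approval where Section 10.1.1 requires it. It needs no new procedure, and the sample size and the primary analysis stay as they are.

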## 6.5. Treatment of Overdose

Overdosing with plasma is not relevant. TACO or excess/perturbed fluid-balance will be considered under adverse events.

# 6.6. Concomitant Therapy

Any medication or vaccine that the participant is receiving at the time of enrollment or receives during the study must be recorded along with:

- Reason for use
- Dates of administration including start and end dates
- Dosage information including dose and frequency

The Medical Monitor should be contacted if there are any questions regarding concomitant or prior therapy.

No medication is contraindicated.

# 7. Discontinuation of Study Intervention and Participant Discontinuation/Withdrawal

## 7.1. Discontinuation of Study Intervention

In this study there is only one intervention performed (plasma transfusion) directly after the informed consent has been obtained.

## 7.2. Participant Discontinuation/Withdrawal from the Study

In cases when the patient withdraws his/her consent:

- A participant may withdraw from the study at any time at his/her own request or may be withdrawn at any time at the discretion of the investigator for safety, behavioral, or compliance reasons. This is expected to be uncommon.
- At the time of discontinuing from the study, if possible, an early discontinuation visit should be conducted, as shown in the SoA. See SoA for data to be collected at the time of study discontinuation and follow-up and for any further evaluations that need to be completed.
- The participant will be permanently discontinued from the study at that time.
- If the participant withdraws consent for disclosure of future information, the sponsor may retain and continue to use any data collected before such a withdrawal of consent.

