## 8.3.1. Frequency for Collecting AE and SAE Information

All SAEs will be collected from the start of intervention until the end of the study period (day 60). Medical occurrences that begin before the start of study intervention but after obtaining informed consent will be recorded as Medical History/Current Medical Conditions, not as AEs.

All SAEs will be recorded and reported to the medical monitor immediately and under no circumstance should this exceed 24 hours. The investigator will submit any updated SAE data to the sponsor within 24 hours of it being available.

Investigators are not obligated to actively seek information on AEs or SAEs after conclusion of the study participation. However, if the investigator learns of any SAE, including a death, at any time after a participant has been discharged from the study, and he/she considers the event to be reasonably related to the study intervention or study participation, the investigator must promptly notify the sponsor.

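### Section 7.2 merges consent withdrawal with investigator withdrawal and, as written, discontinues both permanently; in a single-transfusion trial this can end active AE/SAE detection and secondary assessments before day 60

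*Protocol*

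**What the plan says.** Section 7.2 opens with "In cases when the patient withdraws his/her consent". The first item of the list beneath it goes further and says that a participant "may be withdrawn at any time at the discretion of the investigator for safety, behavioral, or compliance reasons", adding "This is expected to be uncommon". Later in the same list: "The participant will be permanently discontinued from the study at that time".

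For data after that point, 7.2 asks for an early discontinuation visit where feasible and sends the reader to the Schedule of Activities (SoA) to find out what is recorded then and afterwards.

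Section 7.1 describes the exposure: "In this study there is only one intervention performed (plasma transfusion) directly after the informed consent has been obtained".

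Section 8.3.1 sets the safety window: "All SAEs will be collected from the start of intervention until the end of the study period (day 60"). It also says: "Investigators are not obligated to actively seek information on AEs or SAEs after conclusion of the study participation".

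**The concern.** Withdrawing a participant from a study makes sense where further doses can be avoided. Here there is a single transfusion. Once it has been given, and throughout in the control arm, withdrawal from the study cannot reduce exposure to the study product. It spares the participant some procedures and otherwise ends scheduled observation.

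The possible losses are AE/SAE ascertainment and the secondary and exploratory measurements: PCR, oxygen, NEWS, CRP and lymphocytes. Safety is named in the trial title, and incidence of adverse events is a listed endpoint. The protocol itself foresees late events: delayed adverse events (8.2), a theoretical antibody-dependent enhancement (2.3.1), delayed hemolysis and transfusion-transmitted infection (Appendix 4). The first safety review counts dosed participants with 14 days of safety data (10.1.4), a condition that a recipient withdrawn on day 0 or 1 would not meet. Full Analysis Set membership requires sufficient data (9.3.2), so such a participant could also drop out of the secondary analyses.

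The trial is open label, and a transfusion reaction can occur only in the plasma arm. A withdrawal for safety could therefore be related both to outcome and to arm. An analysis plan cannot recover data that were never collected, so this has to be settled in the protocol.

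**Working it through.** The plan gives no figure for this point, so the check sets the provisions side by side and then counts what one withdrawal can cost.

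**1. Who is covered by permanent discontinuation?**
- Reading A: the items of 7.2 apply to everyone whom the section describes. A participant withdrawn by the investigator is then permanently discontinued.
- Reading B: the lead-in confines the items to withdrawal of consent. The investigator's power to withdraw then sits in the wrong list, and nothing states its consequence or which data continue.

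Reading A contradicts other sections. Reading B leaves a gap. Both need a rewrite.

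**2. What does withdrawal stop?** After the transfusion (7.1), no further study exposure. In controls, none at any time. Before the transfusion it can prevent exposure, because the synopsis allows up to 2 days between randomization and plasma.

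**3. What happens to safety data?**
- 8.3.1 collects all SAEs to day 60, but lifts the duty to look for AEs or SAEs once participation has ended.
- The SoA table has columns for screening, day 0 and days 1, 3, 7, 14, 21, 28 and 60. It has no early discontinuation column and no evaluations after withdrawal. As the table reads, AE/SAE review is marked only at day 60, which a discontinued participant does not reach.

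So 7.2 sends the reader to the SoA for a replacement schedule that the table does not contain.

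**4. What continues regardless?**
- Day 28 and day 60 deaths come from the death registry (8.1), and vital status is sought for all randomized participants (7.3).
- SAEs already reported are followed to an outcome or to loss to follow-up (8.3.3); withdrawal is not listed as an end.
- Related SAEs that the investigator learns of later must be notified (8.3.1).
- An adverse event form is completed when participation ends (6.1), and transfusion reactions go to the hemovigilance system (8.3.6).

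**5. Loss per participant under reading A.** Days of active SAE collection lost = 60 − day of withdrawal. Visits lost = SoA visits after that day. Withdrawal is taken to follow that day's assessments.

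| Withdrawn on day | SAE days lost | Clinical assessments lost (of 6 after day 0) | Swabs lost (of 6) | Blood samples lost (of 4) |
|---|---|---|---|---|
| 0 | 60 − 0 = 60 | 6 | 6 | 4 |
| 1 | 60 − 1 = 59 | 5 | 5 | 3 |
| 7 | 60 − 7 = 53 | 3 | 3 | 1 |
| 28 | 60 − 28 = 32 | 0 | 0 | 0 |

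Section 8.1 omits day 21 for PCR. Counting by 8.1 takes one off the swab column in the first three rows.

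**6. How many participants?** The protocol gives no rate. For scale only, with 506 / 2 = 253 per arm and an assumed 1% to 3% withdrawn this way in the plasma arm: 0.01 × 253 = 2.5 and 0.03 × 253 = 7.6, or roughly 3 to 8 people. The percentages are an assumption, and nothing in the protocol supports them over others.

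**The case against.** The strongest reply is that 7.2 is clumsy rather than harmful. Four stronger readings are tempting, and the protocol does not support them.

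- **That safety follow-up ends.** It does not end altogether. The provisions in step 4 of the working survive withdrawal. Only active detection of new events and the scheduled non-mortality assessments are exposed.
- **That the loss falls on exactly the patients with a safety problem.** Section 6.4 says what follows an adverse event during transfusion: the transfusion stops, the dose given is recorded, and the participant leaves the Per Protocol Set. Withdrawal from the study is not mentioned. It is discretionary under 7.2 and expected to be rare. Behaviour and compliance reasons can arise in either arm.
- **That the comparison is biased towards plasma looking safe.** The reaction that prompts a withdrawal comes before it and can already be recorded. Recipients are watched for 1 hour, when most reactions are expected (8.2). The index event would still count in the incidence, and only later events could be missed. A direction of bias is plausible but not demonstrated.
- **That the only dose has always been given.** Withdrawal can precede the transfusion.

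Two further points have weight. Letting a frail participant stop swabs and blood samples is a real benefit, so a simple deletion of the investigator's discretion would go too far. The SoA also refers to a flow-chart that is not available here, so the absence of the early discontinuation visit is confirmed for the table only.

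These points narrow the concern. They do not restore active AE/SAE detection after an investigator withdrawal, nor settle which of the two readings of 7.2 applies.

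**Conclusion.** The point stands in limited form. Section 7.2 merges two situations that carry different data rights and, read as written, ends study participation in both. That conflicts with SAE collection to day 60 and relies on a visit that the SoA table lacks.

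The exposure per participant is at most 60 days of active SAE collection, six clinical assessments, six swabs and four blood samples, and it shrinks with later withdrawal. This assumes that reading A applies and that sites use the release in 8.3.1. The total number cannot be derived from the protocol.

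The primary endpoint, day 60 mortality, the follow-up of SAEs already reported and the notification of related SAEs learned of later are not affected. Differential loss in the safety comparison is a possibility created by the open-label design, not a demonstrated bias. The correction is worth making because the missing data could be event-related and cannot be recovered at analysis.

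**What to change.** Amend 7.2 and reconcile it with 8.3.1, 8.3.3 and the SoA:

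1. Separate withdrawal of consent by the participant or guardian from a decision by the investigator, each with its own statement of what follows.
2. State that an investigator decision may stop study procedures such as swabs and blood samples, but that the participant stays in the study for AE/SAE collection and vital status to day 60, and for oxygen registration to day 28 (the last scheduled clinical assessment), unless consent is withdrawn.
3. Replace the reference to an early discontinuation visit with the visits already in the SoA.

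This concerns data collection only and leaves decisions about giving or stopping the transfusion as they are. The cost is a wording amendment and continued low-burden observation of what should be a few participants. No visits are added.
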